### **Secondary Objective II -- New users of DEX (DEX+) versus new users of MPRED (MPRED):**

From the patients who enter the cohort, all patients who begin use of DEX or MPRED between the admission date (*Day 0*) and 1 day prior to discharge date (*Day D-1*) or a maximum period of 21 days after admission (*Day 21*). New use will be determined using a 90-day washout period to exclude patients with prior use of either DEX or MPRED during the 90 days prior. If a patient uses both treatments over the course of the admission, they will be assigned to their first qualifying treatment arm. If a patient receives both DEX and MPRED on the treatment index, they will be excluded since the effects or the drugs cannot be disentangled among these patients.

*Table 2: Risk set sampling (RSS) matching criteria*

RSS matching criteria	Variable type	Categories (for categorical) / calipers (for continuous)
Calendar date	continuous	±3 days
Age	continuous	±3 years
Sex	categorical	male, female
Combined comorbidity score over 183d baseline period [ Gagne 2011 ]	categorical	0-1, 2-3, 4-5, 6+
Time since hospital admission	categorical	0-1, 2-3, 4-5, 6 - 9, 10 - 14, 15 - 19, 20+ days
COVID-19 severity at treatment index date, per modified WHO (mWHO) score	categorical	No O2, O2/NIV, IMV (highest recorded from days T-1 to T) [see additional subgroup detail below in section V.D. Subgroups ]

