### D. Subgroups: COVID-19 severity at treatment index

The World Health Organization (WHO) Clinical Characterisation and Management Working Group proposed the WHO Clinical Progression Scale, which was created to classify COVID-19 patient outcomes according to disease progression and severity among ambulatory and hospitalized patients [*WHO Working Group 2020*]. We developed an adaptation of the scale that is a modified version of the WHO scale, referred to here as the mWHO score, to categorize

COVID-19 severity at treatment index among hospitalized patients. This mWHO score restricts to the WHO Scale categories specific to hospitalized COVID-19 patients (categories 4-9 in the original scale), which are then collapsed into three mutually exclusive categories based on supplemental oxygen and other ventilation support requirements (no oxygen, oxygen or NIV, IMV). The scale was operationalized by incorporating data from Day T-1 to Day T to account for the lag time in recording ventilation and oxygen supplementation data in the medical claims and chargemaster data. Patients will be assigned to one of the following mWHO categories based on the highest severity feature recorded from 1 day prior to treatment index to the treatment index date (*Day T-1 to Day T*):

- No oxygen at treatment index or within 1 day prior (No O2)
- Any oxygen or non-invasive ventilation with no record of invasive ventilation at treatment index or within 1 day prior (O2/NIV)
- Any use of invasive mechanical ventilation at treatment index or within 1 day prior (IMV)
- Composite of any O2/NIV or IMV at treatment index or within 1 day prior

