
Pre-admission Covariates (Day -21 to Day -1)
	
COVID-19 symptoms and HCRU prior to the admission date.
	
 
- COVID-19 symptoms: pre-admission COVID-19 symptoms
 
- HCRU: Inpatient hospitalization, emergency room encounter
 

Admission Covariates (Day 0; CED)
	
Demographics, hospital facility characteristics, and COVID-19 severity on the admission date.
	
 
- Hospital and admitting characteristics: Hospital setting type, hospital teaching status, hospital number of beds, admission source, emergency room encounter, ambulance encounter, admission type
 
- COVID-19 severity at admission: mWHO severity categorization on the admission date
 

Pre-treatment Covariates (Day 0 to Day T, inclusive)
	
Treatments administered prior to or concurrent with treatment index date, pre-treatment clinical status, and time from admission to treatment.
	
 
- Pre-treatment COVID-19 status: Highest recorded mWHO severity
 
- Pre-treatment utilization characteristics: Number of days hospitalized, number of days with critical/ICU care, in ICU at treatment index, number of unique department codes, number of unique procedure codes
 
- Demographics: Month of treatment index, age, sex, insurance type, US region
 

*\*Smoking/tobacco use may be under-reported [see section VIII. Limitations for additional detail]*

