### 3. Exploration 3: Defining the time period for measuring a modified version of the COVID-19 severity score published by the World Health Organization (mWHO score) at treatment index

[figure not shown]
**Challenge/goal:** Describe how changing the assessment period for determining mWHO severity categorization used for RSS matching and subgroups (no O2, O2/NIV, IMV) to additionally include days prior to treatment index date (**Day T**) changes the distribution of severity categorization.

**Description of exploration:** We aimed to account for situations where patients received respiratory support in other medical settings (e.g., emergency room), in transit prior to admission, or cases where the billing date for a procedure was captured at a later date than the procedure was performed. We began without an additional lookback evaluating only on treatment index (**Day T**), and additionally including a lookback of 1 day (**Day T-1 to Day T**), 2 days (**Day T-2 to Day T**) or 3 days (**Day T-3 to Day T**) prior to treatment index. We also considered looking forward in time to account for instances where procedure dates were coded on a day after the procedure had been performed, but did not wish to introduce concern for immortal person-time bias.

**Summary of key findings:** *Figure A.2* illustrates how the distribution of mWHO COVID severity categorization shifts when the assessment period looks further back from treatment index date (**Day T**). When the assessment period additionally included a 1-day lookback, a small distribution of patients categorized as no oxygen when the assessment window was only on the day of treatment index (Day T) would shift to O2/NIV (2.5-3.2%) and IMV (0.2%) when the assessment period additionally included a 1-day lookback, and 0.3-0.4% of patients categorized as oxygen would shift to IMV.

**Design decision:** Although shifts identified via this exploration were small, they were considered meaningful. Given the trade-off for reducing misclassification without introducing bias, it was decided that we would extend the lookback to 1 day but not further, assigning the mWHO categorization based on max score between T-1 to T.

*Figure A.2: Distribution of mWHO COVID severity when the assessment period is varied*

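### In Secondary Objective II (DEX+ vs MPRED+), the T-1 to T mWHO category that defines the key subgroups is neither matched on nor listed for the propensity score, although Figure 2 says it is used for matching

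*Protocol*

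**What the plan says.** **Definition.** Section V.D sets the mWHO category (No O2, O2/NIV, IMV) "based on the highest severity feature recorded from 1 day prior to treatment index to the treatment index date". It gives the reason for the extra day as "to account for the lag time in recording ventilation and oxygen supplementation data in the medical claims and chargemaster data". Section III uses this category to define the key subgroups for all three referent groups.

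**Matching.** Table 2 lists the category among the risk-set sampling criteria, as "highest recorded from days T-1 to T". The Primary and Secondary I paragraphs of Section V.C.2 both refer to Table 2. The Secondary II paragraph does not. It takes "all patients who begin use of DEX or MPRED between the admission date" and a later limit, applies the 90-day washout, and assigns patients to their first qualifying drug. Section III calls this a traditional new-user design.

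**Propensity score.** Table 3 has two mWHO entries: "mWHO severity categorization on the admission date" and, over Day 0 to Day T, "Highest recorded mWHO severity". It also lists "in ICU at treatment index", days of critical care, and clinical markers such as ARDS, shock and organ support up to Day T. It has no T-1 to T mWHO entry.

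**Figure 2.** The mWHO row (T-1 to T) says the score serves both matching and subgrouping of DEX+ and referent patients. The figure's referent groups include MPRED+.

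**The concern.** Respiratory support around the day of treatment start plausibly affects both the choice between two corticosteroids and the risk of death. In the non-user comparisons, exact risk-set matching handles it at the resolution of the subgroup definition. In DEX+ vs MPRED+, as Section V.C.2 is written, it is handled only through correlated terms. A DEX+ patient in one severity category could then be paired with an MPRED+ patient in another. Table 4 row 3 would have no named row showing this, because Table 3 does not list the variable. Nor would the diagnostic gate stop it: Section VI.B ties progression to the primary objective in the overall cohort, and Section VI.A only promises an attempt at the criteria for secondary objectives.

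**Working it through.** **1. Where each severity measure enters**

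| Measure | DEX+ vs CSI- and DEX- | DEX+ vs MPRED+ |
|---|---|---|
| mWHO, T-1 to T | Risk-set match (Table 2) | None in Section V.C.2 or Table 3; matching according to Figure 2 |
| mWHO, Day 0 | PS list | PS list |
| mWHO, maximum Day 0 to T | PS list | PS list |
| ICU status at T | PS list | PS list |

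The only contradiction in the table is in the first row, last column.

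**2. How far the two windows differ**

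For T of 1 or more, Day 0 to T contains T + 1 days and T-1 to T contains 2. The days in the first but not the second number (T + 1) - 2 = T - 1.

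- T = 1: 0 days; the windows are identical.
- T = 2: 1 day (Day 0).
- T = 7 (IMV subgroup median, DEX-): 6 days.
- T = 9 (IMV subgroup median, DEX+): 8 days.

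The medians come from Table A.3, which describes a DEX+ vs DEX- cohort from an earlier data cut with 62 IMV patients per arm. If that table counts the admission day as day 1, the last two results fall to 5 and 7.

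**3. What the substitute misses**

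Take two hypothetical patients who start treatment on Day 9. Patient A is on IMV from Day 0 to Day 9. Patient B is on IMV from Day 0 to Day 3 and on oxygen from Day 4 to Day 9.

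- Day 0 mWHO: IMV for both.
- Maximum, Day 0 to T: IMV for both.
- T-1 to T mWHO: IMV for A, O2/NIV for B.

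The two patients agree on both mWHO terms in Table 3 yet belong to different subgroups. ICU status at T and ICU days may separate them in part.

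**4. Where it bites**

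Inside a single-level subgroup everyone shares the T-1 to T category, so it cannot be unbalanced. The exposed estimates are the overall DEX+ vs MPRED+ comparison and the composite O2/NIV/IMV subgroup, which mixes two levels.

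**5. A separate, smaller matter: Day T alone against T-1 to T, all comparisons**

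Exploration 3 (Appendix A.3) reports that adding Day T-1 moves 2.5-3.2% from no O2 to O2/NIV and 0.2% from no O2 to IMV, and that "0.3-0.4% of patients categorized as oxygen would shift to IMV". Its denominators are not stated.

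- Denominator is all patients: 2.5 + 0.2 + 0.3 = 3.0% to 3.2 + 0.2 + 0.4 = 3.8% change category.
- Denominator is the starting category (Table A.3 shares of 59.7% and 32.2%): 0.597 × 2.7 + 0.322 × 0.3 = 1.7% to 0.597 × 3.4 + 0.322 × 0.4 = 2.2%.
- If the two ends of the first range were the two arms (an assumption), the absolute standardized difference is |0.030 - 0.038| / √[(0.030 × 0.970 + 0.038 × 0.962) / 2] = 0.044, below the 0.10 limit.
- Share of the IMV subgroup resting on a T-1 record only, using 3.4% IMV: (0.2 + 0.4) / 3.4 = 17.6% at most. With starting-category denominators, and 3.4% read as the Day T share, the lowest value is 0.216 / (3.4 + 0.216) = 6.0%, where 0.216 = 0.597 × 0.2 + 0.322 × 0.3.

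These figures mix data cuts, and the Table A.3 shares sum to 95.3%.

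**The case against.** The best defence is that severity in Secondary II is already well covered. The PS list has mWHO on Day 0, the Day 0 to T maximum, ICU status at T, ICU days and several markers of organ failure. More than 80% of DEX initiators start within one or two days of hospitalization (Section V.C.2), where the windows coincide or differ by a day. Section VI.A also allows subgroup-specific PS models, which would match within category, and covariate adjustment for residual imbalance. Table 2 is printed directly below the Secondary II paragraph, and Figure 2 may simply state the intent.

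Much of this stands, and it keeps the point modest. But the early-start figure is for DEX overall, not for MPRED or the IMV subgroup. The subgroup-specific models are optional. Adjustment can only answer an imbalance that is tabulated. If Figure 2 states the intent, Section V.C.2 needs to say so.

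A reader might go further and infer that severity at treatment start is never balanced in any comparison, or that patients already off a ventilator are matched as if still on it. The documents do not support either reading. The matched window contains Day T, and Table 3 adds single-day terms for admission mWHO and ICU status at index. The T-1 day changes the category for only about 2-4% of patients. A missing Day T record need not mean that support had stopped, since chargemaster diagnoses are generally dated only at admission and discharge (Section V.D). The one-day lookback was a deliberate choice, also meant to capture support given in the emergency room or in transit.

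**Conclusion.** The point holds for Secondary Objective II. As Section V.C.2 and Table 3 stand, the category that defines the key subgroups is neither matched nor a PS term in DEX+ vs MPRED+, and Figure 2 says otherwise. The Day 0 to T maximum is an imperfect substitute, mainly for patients who start late, and the IMV subgroup appears to contain many of these. This assumes that the timing in the earlier DEX+ vs DEX- cohort carries over to DEX+ vs MPRED+. The documents give no MPRED+ severity or timing data, so no bias in the hazard ratio can be calculated. The primary comparison is not affected by this gap.

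Two lesser matters apply to all comparisons. Day T mWHO alone is not tabulated, and an extra balance row would show whether the arms differ on it. And the stated reason for the lookback is only partly right: support given on Day T but dated later falls after T, so a lookback cannot recover it. Exploration 3 considered looking forward for that purpose and declined because of immortal person-time.

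**What to change.** 1. Reconcile Figure 2 with the Secondary II paragraph of Section V.C.2, so that both say whether DEX+ and MPRED+ patients are matched on the T-1 to T mWHO category.
2. Add the T-1 to T mWHO category to Table 3. For Secondary II, enter it in the PS model or match exactly on it. Include it in the Table 4 row 3 balance check, overall and by subgroup; the composite subgroup is where the subgroup check is informative.
3. For all comparisons, report the balance of mWHO on Day T alone as a descriptive diagnostic, noting that a missing Day T record may reflect coding rather than step-down. It need not enter the PS, where it would partly measure coding gaps.
4. Reword the reason in Section V.D: the lookback captures support recorded the day before, including in other care settings, and does not recover Day T support dated after T.

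The cost is one more PS covariate for one secondary comparison and possibly slightly fewer matches. A three-level category takes two model terms, or about 2 × 12 = 24 exposed patients under Table 4 row 4. The category is already derived for subgrouping, and Exploration 3 already derived the Day T value. All of this can be done in the Diagnostic Phase without seeing treatment effects.

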### **E. Primary outcome definition and follow-up (28-day mortality)**

The primary outcome will be inpatient mortality over a 28-day period, sourced from the chargemaster discharge status field. In the primary analysis, follow-up will begin 1 day after treatment index (*Day T+1*) and will continue until the earliest occurrence of the mortality endpoint, 28 days of follow-up reached (*Day T+28*) or discharge from hospital (*Day D*). This approach, referred to here as the “initial-treatment” (IT) approach, assumes patients continue the initial treatment without censoring upon treatment changes, similar to the intent-to-treat approach used in the RECOVERY trial and other randomized controlled trials.

We will also implement an as-treated (AT) censoring approach that additionally censors upon treatment changes. For the DEX+ versus CSI- comparison (**Primary Objective**), this will censor the follow-up of non-users of CSI upon start of any CSI use. For the DEX+ versus DEX- comparison (**Secondary Objective I**), this will censor the follow-up of non-users of DEX upon start of any DEX use. For the DEX+ vs. MPRED+ comparison (**Secondary Objective II**), this will censor the follow-up of patients who start DEX use upon start of any MPRED use and the follow-up of patients who start MPRED use upon start of any DEX use.

A sensitivity analysis will also broaden the follow-up period for capturing inpatient mortality to consider deaths within 60 days after treatment index (T+60) if they occur during the index hospitalization. [see section VII. SENSITIVITY ANALYSES, SA5].

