### III. RESEARCH AIM AND OBJECTIVES

As part of the RCA with the FDA, this study informs the overall project to establish a system for rapid-cycle evaluation, using best practice scientific and operational methods, as applied to relevant and meaningful clinical questions. In this study, we seek to assess the effectiveness of DEX to reduce the risk of inpatient mortality within 28 days among US patients hospitalized with COVID-19 diagnosis or SARS-CoV-2 infection, overall and stratified by COVID-19 severity subgroups [defined according to the presence of encounters indicating supplemental oxygen or ventilation; see *section V.D* for additional subgroup detail], using the HealthVerity database.

The principles outlined by Hernan et al. emphasize the importance of explicitly emulating a hypothetical target trial when planning a RWD analysis to yield RWE [Hernan, Robins 2016; Hernan, Sauer 2016]. Although we reference the UK RECOVERY trial as a basis for comparison [RECOVERY 2020], we sought to emulate a hypothetical target trial with varied design elements, and research questions tailored for US practice and US patients. In a sensitivity analysis, we further sought to replicate the RECOVERY trial design elements (to the extent possible) [see *section VII. Sensitivity Analyses, SA8*].

Specifically, among US patients hospitalized with COVID-19 diagnosis or SARS-CoV-2 infection without prior use of any corticosteroid of interest (CSI; DEX, methylprednisolone, prednisone, hydrocortisone) estimate the hazard ratio and corresponding 95% confidence interval for the risk of inpatient mortality within 28 days after treatment initiation, comparing *new use of DEX* with:

- *non-users of corticosteroids (Primary objective I; DEX+ vs. CSI-)*, to evaluate the potential benefit of DEX above ‘standard of care’ inpatient treatment for COVID-19, where ‘standard of care’ excludes all CSIs (DEX, MPRED, PRED, HC).
- *non-users of DEX (Secondary objective I; DEX+ vs. DEX-)*, to evaluate the potential benefit of DEX above ‘standard of care’ inpatient treatment for COVID-19, where ‘standard of care’ excludes DEX but may include those newly treated with a non-DEX CSI (MPRED, PRED, HC). This comparison is most similar to the RECOVERY trial that compared DEX to ‘standard of care’ [RECOVERY 2020].

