**IV. DATA SOURCE**

This study uses de-identified RWD from HealthVerity comprising open and closed Medical claims and includes major payer types (commercial and federal Medicaid and Medicare programs) from all US states and territories, open and closed Medical and Outpatient Pharmacy claims, Laboratory Data including results, and Hospital Chargemaster transactional records that include diagnoses, procedures and treatments for billable inpatient and outpatient hospital encounters. The data elements derived from chargemaster data are listed in Appendix C along with their percent missingness. The database also includes clinical observations as recorded in electronic health records (EHR), where available. The open claims are sourced in near-real-time from practice management systems, billing systems and claims clearinghouses, and the closed claims are sourced from insurance providers and payers. All ages are included in the full database with ages 65 or older over-sampled to account for the under-representation of Medicare aged patients with commercial coverage. The HealthVerity Medical Claims, Pharmacy, Laboratory and Hospital Chargemaster dataset has been used for scientific publications of COVID-19 research [*Burn 2020; Gordon 2020; Harvey 2021; Murk 2020*].

As of **12-March-2021**, the data spans the time period *01-December-2018* to **22-February-2021** (the last date of available data) and included **58,233,249** patients. The data will be updated periodically as new data become available until we are able to achieve sufficient sample size, as defined in the diagnostic checklist of the statistical analysis [see *section VI.B*].

The primary endpoint of 28-day mortality is defined using Inpatient Chargemaster claims with a discharge status of ‘expired’ indicating death. Given that the HealthVerity data source is relatively new, there are no validation studies of this data source yet for mortality or other endpoints. However, use of discharge status to determine mortality endpoints among hospitalized

COVID-19 patients has been used in both in a similar chargemaster data source [*Rosenthal 2020*] and for national surveillance reporting [*CDC-NCHS 2021*].

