We further explored the data given the importance of this variable to our study. When we compared use of discharge status of death to the separate data files from the vendor providing month of death (date of death was redacted for privacy concerns), we found that all patients with a death month indicated also met our endpoint definition. Further, when we compared weekly deaths over time in our overall cohort of patients hospitalized with COVID-19 (reminder that we will not look at death stratified by treatment until after the diagnostic phase is completed), we identified similar trends to that of two external national benchmarks, the Centers for Disease Control {*CDC-NCHS 2021*} and data sourced from State and local health agencies {*NYT 2021*}, providing further assurance of the accuracy of the capture of our endpoint.

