### A. Study design

This study is an observational cohort study using secondary healthcare data. The study diagram and its components are illustrated and further detailed below [*see Figure 2*].

Figure 2. Study diagram

Inclusion/Exclusion Criteria	
COVID-19 confirmation	Hospitalized patients with confirmed COVID-19 (ICD 10 diagnosis: U07.1 or positive or presumptive positive SARS-CoV-2 diagnostic laboratory test result; Day -21 to Day T).
Baseline Exclusion	Exclude patients without activity in the 183 day baseline period (Day -183 to Day -1).
Missing Demographics Exclusion	Exclude patients with missing age, sex, or region on the hospital admission date (Day 0; CED).
COVID-19 Vaccine Exclusion	Exclude patients with any record of a COVID-19 vaccine on or any time prior to the treatment index date given that these patients are assumed to be selectively different (Day S to Day -1).
Treatment Exposure	Hospitalized COVID-19 patients with new use of systemic dexamethasone (DEX+) or referent groups (CSI-, DEX-, MPRED+). Treatment index date (Day T) must occur between hospital admission date (Day 0; CED) and 1 day prior to hospital discharge date (Day D-1).
Treatment Washout	Exclude patients with prior systemic CSI use from all comparisons (Day -90 to Day T-1).
Covariate Assessment	
Baseline	Baseline (pre-admission) comorbidities, co-medications, and healthcare resource utilization (HCRU; Day -183 to Day -1).
Pre-admission	COVID-19-related symptoms, complications, and HCRU leading up to the hospital admission date (Day -21 to Day -1).
On admission	Demographics, facility characteristics, and covariates related to admitting status (Day 0; CED).
Pre-treatment (Inclusive)	Treatments administered prior to or concurrent with treatment index date, pre-treatment clinical status, and time from admission to treatment (Day 0 to Day T).
mWHO Severity	COVID-19 severity per modified version of WHO ordinal scale (mWHO), used for matching and subgrouping of DEX+ and referent patients (Day T-1 to Day T).
Outcome Assessment	
Follow-up	Follow-up window for primary outcome of 28-day inpatient mortality (Day T+1 to the earlier of Day T+28 or D).

*CED, Cohort Entry Date; D, Hospital discharge date; S, Start of available data; T, Treatment index date*

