## C. Study population

### 1. Cohort entry

#### Hospitalized Patients with COVID-19:

Patients will enter the cohort upon the admission date of the first qualifying inpatient hospitalization observed in the hospital chargemaster data. The first eligible cohort entry date is **01-April-2020**, the date when the ICD-10 code for COVID-19 diagnosis was added. The last possible cohort entry date will be 60 days prior to the last date of available data [see *Appendix A.5 Exploration 5* for additional detail justifying this design decision].

COVID-19 confirmation was defined as either of the following occurring between 21 days prior to the hospital admission date and the treatment index date, which is described in section C.2. below (inclusive; **Day -21 to Day T**):

- Outpatient medical encounter prior to or on the admission date or diagnosis 'present at admission' with ICD-10-CM diagnosis of U07.1 for COVID-19, virus identified; OR
- positive or presumptive positive SARS-CoV-2 diagnostic laboratory test result

The decision to include either diagnosis or positive laboratory test results was based on an initial exploration [see justification detail in *Appendix A.1. Exploration 1*].

For the DEX+ versus MPRED+ comparison (**Secondary Objective II**), given the increased use of MPRED earlier on in the COVID-19 pandemic, we may consider delaying the cohort entry to start in May or June pending data exploration.

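### Follow-up for the primary endpoint stops at discharge from the first qualifying stay, so an in-hospital death by T+28 after transfer or readmission is censored, and no analysis recovers it

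*Protocol*

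**What the plan says.** - **Objective (Section III).** The hazard ratio is "for the risk of inpatient mortality within 28 days after treatment initiation". No restriction to a single stay is stated.
- **Endpoint source (Section IV).** "The primary endpoint of 28-day mortality is defined using Inpatient Chargemaster claims with a discharge status of" expired. The sentence names the data field and does not say which stay it is read from.
- **Outcome and follow-up (Section V.E).** "The primary outcome will be inpatient mortality over a 28-day period, sourced from the chargemaster discharge status field". Follow-up starts on T+1 and "will continue until the earliest occurrence of the mortality endpoint, 28 days of follow-up reached", or until discharge (Day D), whichever comes first.
- **Figure 2 (Section V.A).** It agrees: "Follow-up window for primary outcome of 28-day inpatient mortality (Day T+1 to the earlier of Day T+28 or D". Table A.1 in Appendix A says the same.
- **Which stay (Section V.C.1).** "Patients will enter the cohort upon the admission date of the first qualifying inpatient hospitalization observed in the hospital chargemaster data". Day D is therefore the discharge date of that stay.
- **Longer follow-up (Section V.E and Table 5, SA5).** SA5 extends to 60 days, but only for deaths in the index stay.
- **Analysis (Section VI.C).** Person-day rates and Cox hazard ratios, so leaving hospital alive is a censoring time.

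The protocol gives no rule for transfer or readmission. None of SA1 to SA8 counts a death after Day D, and Section VIII does not list the omission as a limitation.

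**The concern.** Take a patient who starts dexamethasone on Day 1, moves to another hospital on Day 4, and is recorded as expired at the end of that second stay on Day 12. She died as an inpatient within 28 days of starting treatment, which is the event the objective describes. Under V.E her observation ends on Day 4, alive.

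This is separate from how discharge home should be handled as a competing event. A cumulative-incidence analysis would also code her as discharged alive on Day 4. Her inpatient course had not ended; only the first billing stay had.

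Cox regression treats such a patient as if she shared the later risk of comparable patients still in the first hospital. Someone transferred for a higher level of care probably does not. If transfer rates also differ between DEX+ and the referent group, the hazard ratio is distorted, and the sign depends on which arm transfers more.

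**Working it through.** **1. Is there room for such deaths?** Appendix A.5 gives a median stay of 6 days and a 95th percentile of 27 days in an exploratory data cut. About half of the stays therefore end well before T+28. How many of those discharges are transfers, and how many are followed by a death in hospital, is not given.

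**2. Does the vendor check settle it?** In Section IV, "we found that all patients with a death month indicated also met our endpoint definition". If that definition means an expired status in any stay, a second-stay death passes the check and is still censored under V.E. If it means the full V.E endpoint, the check is evidence against many missed deaths. The text does not say which, and the vendor file holds only the month of death.

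**3. How large could the effect be?** The protocol states no figure to reproduce, so every input here is an assumption: 28-day inpatient risk of 25.0% in CSI- and 20.6% in DEX+, a share *t* of each arm transferred early, and mortality *m* after transfer.

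True ratio: 20.6 / 25.0 = 0.824.

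Patients censored early leave the risk set, so they come out of numerator and denominator. Per 100 patients per arm:

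ratio = [(20.6 − t_DEX·m) / (100 − t_DEX)] ÷ [(25.0 − t_CSI·m) / (100 − t_CSI)]

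| Transfer, CSI- vs DEX+ | m, both arms | Calculation | Ratio | Shift |
|---|---|---|---|---|
| 4% vs 2% | 40% | (19.8/98) ÷ (23.4/96) | 0.829 | +0.005 |
| 6% vs 2% | 50% | (19.6/98) ÷ (22.0/94) | 0.855 | +0.031 |
| 2% vs 4% | 40% | (19.0/96) ÷ (24.2/98) | 0.802 | −0.022 |
| 3% vs 3% | 40% | (19.4/97) ÷ (23.8/97) | 0.815 | −0.009 |

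The last row is not exactly zero only because *m* is the same in both arms, which assumes no treatment effect in transferred patients. If the ratio of 0.824 also holds in them, DEX+ mortality after transfer is 0.824 × 40% = 32.96%, and equal transfer gives (20.6 − 0.989) / 23.8 = 0.824, no shift. On that same assumption the first row becomes (19.941/98) ÷ (23.4/96) = 0.835 (+0.011) and the second, with DEX+ mortality 0.824 × 50% = 41.2%, becomes (19.776/98) ÷ (22.0/94) = 0.862 (+0.038).

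This is a risk-ratio approximation to what early censoring does to a hazard ratio. It shows order of magnitude and sign only.

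**The case against.** **No contradiction.** A reader might infer that Section IV counts any expired record while V.E counts only the index stay. Section IV does not say that. It names a field, and Figure 2, V.E, Table A.1 and SA5 all describe follow-up that ends at discharge. At most, Section IV leaves the stay unspecified.

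**Not scored as survivors.** A reader might also infer that these patients are carried to day 28 as survivors. In the planned Cox model and person-day rates they are censored at Day D. They would count as non-events only in a simple proportion, for example the Table 4 baseline risk if it is computed that way.

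**Larger ratios are tempting but wrong.** Subtracting the lost deaths while keeping transferred patients in a full 28-day denominator gives (20.6 − 0.8)/(25.0 − 1.6) = 0.846 and (20.6 − 1.0)/(25.0 − 3.0) = 0.891. That does not describe a censored analysis.

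**Operational detail.** How stays are built from billing records may be set out in measure definitions, which Section V offers on request. That is fair for code lists. It is weaker for the date that ends follow-up for the primary endpoint, which V.E fixes without a transfer rule.

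**Confounding control.** Table 3 lists hospital setting, teaching status, bed count and admission source as candidate propensity covariates. These partly address a hospital-level link between steroid use and transfer. They do not restore the uncounted deaths.

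**Capture.** The protocol does not say that receiving hospitals are in the chargemaster data. Some will not be, so the number of recoverable deaths is unknown.

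**Conclusion.** The point holds as a gap between the objective and the end of follow-up. A patient who dies in hospital by T+28 in a later stay meets the Section III objective and is censored at Day D. No planned analysis shows how often this happens, and Section VIII does not mention it. The censoring is unlikely to be non-informative.

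The size cannot be derived from the protocol. Under assumed transfer of 4% vs 2% to 6% vs 2%, higher in CSI-, the shift is roughly 0.005 to 0.03 on the ratio scale, or slightly more if the treatment effect persists after transfer. It reverses sign if DEX+ patients transfer more, and it is near zero if transfer is equal. These shifts are modest beside the planning hazard ratio of 0.8. The case for change rests on low cost and a clearer endpoint, not on a demonstrated large bias. The documents support neither a contradiction between Sections IV and V.E nor a claim that these patients are scored as survivors.

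**What to change.** 1. **Section V.E and Figure 2.** Define Day D as the end of the inpatient episode: join the same patient's chargemaster stays when the next admission falls on the same or next calendar day, and take discharge status from the last stay in the chain. Say whether this Day D also governs the treatment-index window in Section V.C.2, which currently runs to Day D-1, or applies to follow-up only.
2. **Table 5.** Add one sensitivity analysis that counts an expired status in any inpatient stay up to T+28, including readmissions.
3. **Reporting.** Tabulate index discharge status by arm. Because this shows deaths by treatment, it belongs in the Inferential Phase; pooled transfer counts can be reviewed earlier.
4. **Section VIII.** State that transfers to hospitals outside the chargemaster data remain censored, and report how many there are.
5. **Section IV.** State which stay or stays the death-month check covered.

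The cost is protocol wording and programming. The protocol already reads discharge status and uses more than one hospitalization per patient (Section V.C.1 and Table 3), so no new data source is needed. A next-day readmission after going home would be joined as if it were a transfer, and deaths in uncaptured hospitals stay invisible. The change should be made before the Inferential Phase, while outcomes by treatment are still unseen.
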